1. Evidence that the HR is not constant over the period of follow up will be assessed and the risk of diabetes will be assessed in a PH model. The primary test for treatment effect is based on the Cox model, which assumes a proportional hazard between treatment groups. If there is a true treatment effect but it is not proportional over the follow-up period the test will have substantially less statistical power than stated in the statistical section of the protocol. Therefore, to establish a reasonable guide to pursue the possibility of a non-proportional treatment effect we will use the guideline requiring a significance level of 0.10 or less of the LRT from the standard Cox model. Graphical diagnostics using Schoenfeld residuals will be employed to explore evidence for a monotonically decreasing effect of treatment over the follow-up period. Also, plotting the Kaplan-Meier time-to-AGT rates by treatment group on the log-log scale will provide visual assessment of any diminishing effect of treatment (equal distance separation of curves indicates proportional hazard). We will characterize any such decreasing effect of treatment by model parameterization with monotonically decreasing benefit over the follow-up time. Initially, a treatment interaction with log-transformed time-on-study will be fit to the data and the log likelihood improvement in the fit noted. Other time transforms will be explored only to characterize mathematically the rate of the diminishing effect. Of particular interest will be characterizing the point in follow-up where the hazard ratio is 1. Any variations in proportional hazards other than a monotonically decreasing effect will not be of interest because of the possibility that it is simply random error.

5. Study Power and Sample Size

This study has been designed to provide 83% power to detect a 50% risk reduction in the hazard rate for progression to Stage 2 or 3 T1D (abnormal glucose tolerance or diabetes diagnosis) using a two-sided test at the 0.05 level after a minimum of two years of follow-up on all participants and an expected total study duration (accrual and follow-up) of six years. We note that if accrual is more rapid than expected, minimum follow-up on participants may need to be extended in order to meet the number of events required for the final analysis.

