A total of 201 participants will be randomized in a 2:1 allocation to treatment with hydroxychloroquine (n=135) vs. placebo (n=66). Randomization will be conducted using block randomization with variable block sizes with stratification on (1) whether or not participants have been previously treated for T1D prevention, and (2) age group (< 8 years old vs. 8 years old or older).

The assumptions underlying the estimated sample size for this design are: (1) 40% two-year event rate in the placebo group, (2) detectable hazard ratio of 0.50 (i.e. 22.5% two-year event rate) in the hydroxychloroquine group, (3) less than a 10% two-year dropout rate in both groups, and (4) survival curves which are consistent with exponential survival distributions. Even testing for variable proportions of each stratum and with slight variation in the expected hazard rates for the placebo group across the strata, our proposed sample size of 201 participants will provide at least 83% power to detect a hazard ratio of 0.50 in the time to T1D stage progression between the two treatment groups using a stratified Cox regression model⁷⁵.

Under the above assumptions, the target total number of events is equal to 80; i.e., the final analysis will be conducted once 80 events (confirmed abnormal glucose tolerance, diabetes) have been observed. If the accrual rate is 50 patients per year, with the above assumptions it is estimated that the enrollment period will last approximately 4 years with a total study duration of approximately 6 years (4 years of accrual + minimum of 2 years of follow-up) to provide a sufficient number of events to detect the assumed difference.

The final test of significance up to the six-year time point will employ group sequential critical values to protect against inflation in the type I error probability due to interim assessments of the emerging data for review by the DSMB (see Section 8.5).

Note the accrual period and the study sample are only projections, since the actual accrual rate and the loss-to-follow-up rate are unknown. As the study progresses, more accurate projections of the study end date will be computed based on the observed rate of enrollment, the observed number of events, and the observed rate of loss-to-follow-up. These data will be provided to the DSMB and the TrialNet governing body, and if need be, this document will be amended.

6. Interim Monitoring Plan

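### The only model the SAP names for finding when the hazard ratio reaches 1 cannot represent a lasting partial benefit, so the crossing time cannot tell waned from lost effect

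*SAP*

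**What the plan says.** Item 1 of the additional pre-specified analyses in SAP section 4.4 deals with a hazard ratio that changes over follow-up. It is entered through a 0.10 guideline on the likelihood ratio test from the standard Cox model, followed by Schoenfeld residual plots and log-log Kaplan-Meier plots. It then continues: "We will characterize any such decreasing effect of treatment by model parameterization with monotonically decreasing benefit over the follow-up time". The first fit is specified: "Initially, a treatment interaction with log-transformed time-on-study will be fit to the data and the log likelihood improvement in the fit noted". Other time transforms may be tried, but none is named, and their stated use is to describe how fast the effect declines. The item then gives its target: "Of particular interest will be characterizing the point in follow-up where the hazard ratio is 1". Departures other than a monotone decline are set aside as possibly random.

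The item does not say which fitted model supplies the crossing time, what evidence for the interaction is needed, what interval goes with the time, or what to do if the effect weakens but persists. Protocol section 8.2 treats non-proportionality more broadly, as post-hoc work on decaying, diverging or crossing effects.

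**The concern.** A time at which the hazard ratio equals 1 will be read as the time at which hydroxychloroquine stops working, and later times as possible harm. The log-time form produces such a time whenever the fitted effect declines from benefit, whether the truth is a lost effect or a benefit that weakens and then holds. A declining effect is exactly the situation this item is written for. If the output looks much the same under both truths, a positive trial could be described as showing a temporary benefit when a lasting one fits the data equally well.

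**Working it through.** **Inputs.** SAP section 5 gives 201 participants (135 and 66), 80 events in total, 4 years of accrual with at least 2 years of follow-up, under 10% two-year dropout, "40% two-year event rate in the placebo group", "detectable hazard ratio of 0.50 (i.e. 22.5% two-year event rate) in the hydroxychloroquine group", and "survival curves which are consistent with exponential survival distributions". SAP section 3 puts event times on a 6-month grid.

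**1. The plan's own power.** The SAP states: "This study has been designed to provide 83% power to detect a 50% risk reduction in the hazard rate", "using a two-sided test at the 0.05 level". Schoenfeld's formula gives sqrt(80 × 2/3 × 1/3) × |ln 0.50| = 4.216 × 0.693 = 2.923. Subtracting 1.960 leaves 0.963, and the power is Φ(0.963) = 83.2%. With the final boundary of 1.969 it is 83.0%. The placebo hazard is −ln(0.60)/2 = 0.2554 per year. Half of that gives 1 − exp(−0.2554) = 22.5% at two years. The design figures reproduce.

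**2. Algebra.** The named model is ln HR(t) = b + g·ln t, so HR = 1 at t* = exp(−b/g). For any g > 0 there is exactly one finite crossing. As t grows, HR(t) rises without limit, so no plateau is possible.

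Illustration (time points chosen here): a log-time curve through HR 0.30 at 0.5 years and 0.60 at 2 years has g = ln(0.60/0.30)/ln(2/0.5) = 0.5, so HR(t) = 0.30 × sqrt(t/0.5). This equals 1 at t = 0.5 × (1/0.30)² = 5.6 years, about the end of follow-up, even if the true ratio stays at 0.60 for good.

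**3. Simulation.** Design inputs as above, with these assumptions: uniform accrual, exponential dropout of 10% at two years, an unstratified Cox model and analysis at the 80th event. The 0.10 guideline is read as the treatment test, in favour of drug. There were 1,500 to 4,000 trials per scenario. Entries are the share of qualifying trials with g > 0 and t* inside follow-up. Ranges come from separate runs. Some counted crossings to the last event and others to the longest follow-up, which accounts for part of the spread.

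| True hazard ratio | Continuous times | 6-month times |
|---|---|---|
| 0.50 throughout | 2.5–3.9% | 6–8% |
| 0.65 throughout | 6.5% | 10.5% |
| 0.30 to 1 year, then 0.60 | 16–18.5% | 27–33% |
| 0.35 to 1.5 years, then 0.75 | 21–25% | 35–42% |
| 0.30 to 1 year, then 0.70 | 30% | 47% |
| 0.40 to 2 years, then 1.0 (benefit ends) | 23–27% | 42–47% |

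At a constant 0.50, about half of qualifying trials (49% and 50%) fit a decline. The median crossing among these is about 245 years (continuous) or 38 years (6-month times), far outside follow-up.

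**4. What a crossing tells the reader.** On 6-month times, in one set of runs counted to the last event, a crossing is 42/35 = 1.2 times as likely when benefit ends as under 0.35 then 0.75, and 42/27 = 1.6 times as likely as under 0.30 then 0.60. Against a constant 0.50 the ratio is 42/6.3 = 6.7. A crossing is evidence that the effect has waned. It is little evidence that the effect has ended.

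**5. Would an interaction threshold be enough?** Requiring p ≤ 0.10 for the interaction lowers false crossings at constant 0.50 to 2.8% and 3.5%. Across the waning-to-plateau shapes in that run 17% to 37% remain, and for 0.35 then 0.75 on 6-month times 29% remain. The threshold detects waning, but the log-time form still forces the crossing.

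**6. What 80 events can support.** If a two-period split leaves 40 events in each period, the standard error of ln HR in a period is about 1/sqrt(40 × 2/9) = 0.335. The 95% limits are then the estimate divided and multiplied by exp(1.96 × 0.335) = 1.93. A late estimate of 0.75 has limits of about 0.39 to 1.45, and one of 1.0 about 0.52 to 1.93. The data will seldom separate the two, and a bare crossing time hides this.

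**The case against.** The item is descriptive. It changes no primary test, alpha, sample size or stopping rule, and protocol section 8.2 already classes such modelling as post-hoc. The SAP looks for a point inside follow-up, which rules out the many forced crossings decades away. It does not say that the log-time fit supplies the point: that fit comes first, and a transform such as 1/t would allow a plateau. The residual and log-log plots come before the modelling, whereas the simulation counts every fitted decline, so its rates are upper bounds on what careful analysts would report. The waning shapes come from neither document.

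All of this stands as a limit on size. A reader might infer from the algebra, and from about half of fitted effects declining by chance, that the SAP will often announce a false end of benefit in any positive trial. The documents do not support that. Under their own constant hazard ratio the rate inside follow-up is about 3% to 8%, and the text asks for nothing outside follow-up.

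The objection does not supply what is missing. No decision rule is attached to the plots, no form that can level off is named, and nothing in the item asks for uncertainty around the crossing. On the reading used here, the 0.10 guideline tests treatment, not the change in its effect.

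**Conclusion.** The point holds in a limited form. As written, the crossing time cannot distinguish a lasting reduced benefit from a lost one. For the two main plateau shapes (0.35 then 0.75, and 0.30 then 0.60), a false crossing inside follow-up appears in 16% to 25% of qualifying trials with continuous times and in 27% to 42% with the SAP's 6-month times. The first shape comes close to the rate seen when benefit really ends, and the second reaches about two thirds of it. Under the plan's constant hazard ratio the problem is minor.

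The sizes rest on the assumed shapes, on the simulation assumptions listed above, and on applying the item to the primary endpoint. They also rest on the 80-event trigger. SAP section 7 (Timing of Analyses) gives a different trigger, 64 to 70 placebo-group events, and the two must be reconciled separately. The change is worth making before unmasking because the output is easily over-read, but the primary conclusion does not depend on it.

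**What to change.** Replace the HR = 1 sentence in SAP section 4.4, item 1, with the following.

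- Report HR(t) with pointwise 95% confidence limits over observed follow-up, from the log-time model and from one prespecified form that can level off, for example a hazard ratio constant within two periods split at a time fixed before unmasking.
- Give a crossing time only with a confidence interval. Call it not estimable when the interval is not contained in observed follow-up, and quote nothing beyond the last event time.
- State that not estimable does not mean that benefit persists. The two HR(t) displays carry the interpretation.

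Do not add a rule that benefit has ended only if the lower 95% limit of HR(t) exceeds 1. That tests for harm, not for loss of benefit. In simulations where the hazard ratio truly returned to 1, it triggered in only about 0.2% to 3.5% of qualifying trials, and in 6% when the late ratio was 1.3. If the crossing interval is taken as the set of times at which the pointwise limits include 1, containment in follow-up is nearly as demanding. That is acceptable for deciding whether to print a time, but not for deciding whether benefit has ended.

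The cost is a few sentences and a few lines of code. The downside is that, with 80 events, the SAP will usually be unable to name a time when benefit ends.

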## **4.3. Randomization and Baseline visits**

Participants will be randomized to either the treatment arm or the placebo arm. Randomization must occur within 7 weeks of a normal OGTT in order to ensure that participants have normal glucose tolerance, and study drug administration must occur within 4 weeks after randomization.

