## **8. STATISTICAL CONSIDERATIONS AND ANALYSIS PLAN**

This is a randomized, double-blinded, placebo-controlled clinical trial designed to assess the impact of hydroxychloroquine to reduce the risk of progression from Stage 1 T1D (multiple autoantibodies, normal glucose tolerance) to Stage 2 (abnormal glucose tolerance) or Stage 3 (clinical diagnosis of diabetes). Eligible participants will be randomized in a 2:1 allocation ratio to treatment with hydroxychloroquine vs. placebo. Randomization will be stratified by two factors to ensure balance in the proportions who are randomized to each of the treatment arms: (1) prior enrollment on a T1D prevention trial and (2) age (<8 vs. ≥8 yrs. old). Specifically, participants will be randomized to hydroxychloroquine vs. placebo with stratification on whether they: (1) had prior enrollment on a T1D prevention trial and received placebo vs. had prior enrollment on a T1D prevention trial and received active therapy vs. had no prior enrollment on a T1D prevention trial, and (2) are younger than 8 years old vs. 8 years old or older. Age is a known significant factor in relation to clinical outcomes of interest even in the T1D prevention setting. Further, this cutoff of 8 years old at study entry was selected based on analyses that showed a significant effect modification on clinical outcomes based on this.

Analyses of study data will be conducted to address the primary and secondary objectives of the trial, other stated objectives, and other interrelationships among elements of study data of interest to the investigators and of relevance to the objectives of the study. Analyses by age, gender, and race/ethnicity, as appropriate, are also planned.

All analyses will be conducted under an intention-to-treat principle, whereby all outcome data in all randomized participants will be included in all analyses, as appropriate. Details of the analysis can be found within the statistical analysis plan.

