### **8.1. Primary Outcome**

The primary outcome is the elapsed time from random treatment assignment to the development of confirmed abnormal glucose tolerance or clinical diabetes among those enrolled in the primary analysis cohort consisting of participants with islet cell autoimmunity and absence of metabolic abnormalities (normal OGTT). The date of the confirmatory abnormal OGTT or diabetes will be considered as the date of reaching these study endpoints. It is expected that abnormal glucose tolerance will be detected prior to diabetes onset by OGTT; however, the presence of diabetes, without a previous abnormal

OGTT, is also considered an endpoint.

While the hydroxychloroquine prevention study is ongoing, any participant who has progressed to abnormal glucose tolerance will have met the primary endpoint criteria. These participants who have developed abnormal glucose tolerance but have not progressed to Stage 3 T1D will have the option to remain in this study without further therapy; they will receive close monitoring and safety assessments until the development of Stage 3 T1D (clinical diabetes) or until they enroll in another clinical trial, whichever comes first.

The study endpoint is realized with either confirmed OGTT criteria for abnormal glucose tolerance or diabetes or clinical criteria for diabetes.

OGTT criteria for abnormal glucose tolerance or diabetes:

The presence of an OGTT consistent with impaired glucose tolerance or diabetes on two sequential dates. A participant with abnormal glucose tolerance or diabetes on an OGTT should undergo a repeat OGTT as soon as possible, but no less than one day apart. Aim to repeat within one month.

The definition of abnormal glucose tolerance is:

- a. Fasting plasma glucose  $\geq 110$  mg/dL (6.1 mmol/L) and  $< 126$  mg/dL (7.0 mmol/L), or
- b. 2 hour plasma glucose  $\geq 140$  mg/dL (7.8 mmol/L) and  $< 200$  mg/dl (11.1 mmol/L), or
- c. 30, 60, 90 minute plasma glucose during OGTT  $\geq 200$  mg/dL (11.1 mmol/L).

Criteria for Diabetes Diagnosis:

- A. Diabetic Ketoacidosis (DKA) or unequivocally symptomatic\* AND at least one of the following:
- 1) Random glucose  $\geq 200$  mg/dl (11.1 mmol/L) OR
  - 2) Fasting Glucose  $\geq 126$  mg/dl (7.0 mmol/L) OR
  - 3) OGTT = diabetic\*\* OR
  - 4) HbA1C  $\geq 6.5\%$ .

\*Unequivocal symptoms: Severe/persistent polyuria, polydipsia and/or significant unexplained weight loss

\*\*A diabetic OGTT is defined as:

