## **8.6. Withdrawal Criteria – Individual Participants**

An intention-to-treat approach will be used in these analyses. Participants will not be replaced. All data acquired prior to termination for the reasons outlined below will be included in the primary analysis unless a participant withdraws consent for the use of those data. Every effort will be made to conduct a final study visit with the participant, and participants will be followed clinically until, if applicable, all potentially study-related adverse events resolve.

- Withdrawal of consent by the participant
- Withdrawal of the participant by the investigator
- Intercurrent illness or event that precludes further visits to the study site or ability to evaluate disease.

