TN-22 Statistical Analysis Plan

TRIAL FULL TITLE	HYDROXYCHLOROQUINE FOR PREVENTION OF ABNORMAL GLUCOSE TOLERANCE AND DIABETES IN INDIVIDUALS AT-RISK FOR TYPE 1 DIABETES MELLITUS (Protocol TN-22)
EUDRACT NUMBER	2018-000659-42
Phase	Phase IIb
SAP VERSION	Version
ISRCTN NUMBER	
SAP VERSION DATE	September 26, 2022
TRIAL STATISTICIAN	[name]
TRIAL CHIEF INVESTIGATOR	[name] and [name]
SAP AUTHOR	[name]

Contents

Table of Contents	Error! Bookmark not defined.
1. Abbreviations and Definitions.....	3
2. Introduction	3
3. Primary Analysis	4
4. Secondary Outcomes and Analyses	4
5. Study Power and Sample Size.....	6
6. Interim Monitoring Plan	7
7. General Considerations	7
8. Safety Analyses.....	8
9. Reporting Conventions.....	9
10. Per Protocol Analysis	9
11. Technical Details.....	9
12. References.....	10

1. Abbreviations and Definitions

AE	Adverse Event
ADA	American Diabetes Association
AGT	Abnormal Glucose Tolerance
AUC	Area Under the Curve
BMI	Body Mass Index
DSMB	Data Safety Monitoring Committee
ITT	Intent to Treat
OGTT	Oral Glucose Tolerance Test
PH	Proportional hazards
SAE	Serious Adverse Event
SAP	Statistical Analysis Plan
T1DM	Type 1 Diabetes Mellitus

2. Introduction

Preface

While the mechanism of action of hydroxychloroquine is poorly understood, it appears to act on autoimmune responses; thought to target B cell responses. In particular, hydroxychloroquine has been shown to decrease cellular activation, including hindering of antigen presentation to CD4+ T cells and reducing the expression of the CD4+ T cell activation marker CD154^{30,31}. Hydroxychloroquine is also thought to have a number of other immune actions that may lead to decreased autoantibody production, including (i) alkalinization of intracellular vacuoles leading to inhibition of proteolysis, chemotaxis, phagocytosis, and antigen processing³², (ii) reduction of macrophage-mediated cytokine production³³ and (iii) inhibition of function of toll-like receptors³⁴.

Purpose of the analyses

Analyses of study data will be conducted to address all objectives and other interrelationships among elements of study data of interest to the investigators and of relevance to the objectives of the study. Analyses by sex, age, and race/ethnicity are also planned.

All primary analyses will be conducted under the intention-to-treat principle whereby all outcome data in all randomized subjects will be included, regardless of treatment compliance.

Primary Outcome

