A formal interim analysis of efficacy will be conducted when 50% of events (i.e., information fraction = 0.50) have been observed; i.e., we will conduct an interim analysis to compare the two treatment arms when 40 participants enrolled on this trial have a reported progression to Stage 2 or 3 T1D. To preserve the Type I error rate control for each of these comparisons on superiority, the Lan-DeMets error spending rate function with the O'Brien-Fleming boundaries is utilized. If these boundaries are crossed, then the TrialNet DSMB will determine if accrual to that arm should be suspended and/or if treatment of participants should be modified based on these results⁷⁶. The interim and final analysis boundaries and characteristics were generated using the East 6 clinical trial software program (version 6.3, Cytel Inc).

Information fraction	Cumulative events	Alpha spent	Efficacy boundary (p-value)
0.50	40	0.0031	2.963 (or -2.963)
1.00	80	0.00153	1.969 (or -1.969)

The DSMB may terminate the trial prematurely if a statistically significant effect is observed and it is considered that all major trial objectives have been met.

In lieu of a formal futility rule at the interim analysis (i.e., 50% information), we will utilize conditional probability methods to assess the probability that hydroxychloroquine will delay time to T1D stage progression based on the data observed at that point if the observed hazard ratio is >1.05 (i.e., in favor of placebo).

The DSMB will also consider early termination due to absence of a treatment effect (i.e., futility) based on computations of conditional power conducted both under the initial study design and under the current trend of the data⁷⁷.

7. General Considerations

1. Analysis Populations

The Intention to Treat Population (ITT)

The intention to treat population comprises all randomized (as planned) subjects.

Full Analysis Population

The Full Analysis Set (FAS) will comprise all subjects who received any study drug and who participated in at least one post-baseline assessment. These will be analyzed as randomized. FAS will be the primary efficacy population. So, FAS is a subset of ITT.

Per Protocol Population

The Per Protocol Set (PPS) will comprise all subjects who did not substantially deviate (defined as greater than or equal to 75% protocol compliance) from the protocol as to be determined on a per-subject basis before data base lock and unblinding.

Safety Population

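### The SAP assigns the primary analysis to two different populations: all randomized participants in section 2, and a dosed and assessed subset in section 7

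*SAP*

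**What the plan says.** SAP section 2 (Purpose of the analyses) gives an unqualified rule: "All primary analyses will be conducted under the intention-to-treat principle whereby all outcome data in all randomized subjects will be included". It adds that compliance with treatment does not matter.

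SAP section 7, item 1 (Analysis Populations) defines the intention-to-treat set as all randomized subjects. It then defines a second set: "The Full Analysis Set (FAS) will comprise all subjects who received any study drug and who participated in at least one post-baseline assessment". Of that set it says "FAS will be the primary efficacy population", and it notes that the FAS is a subset of the intention-to-treat set.

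SAP section 3 (Primary Analysis) specifies the test but not the population. SAP section 6 sets the interim look for the time "when 40 participants enrolled on this trial have a reported progression to Stage 2 or 3 T1D", which counts enrolled participants rather than FAS members.

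Protocol section 8 says "all outcome data in all randomized participants will be included in all analyses, as appropriate" and leaves analysis details to the SAP. Protocol 8.6 says "An intention-to-treat approach will be used in these analyses. Participants will not be replaced". Protocol 7.2.4.1 also calls the trial an intention-to-treat study.

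**The concern.** Both SAP rules are current, and they name different people. FAS membership depends on two things that happen after randomization: taking at least one dose and attending at least one later assessment. The outcome clock starts earlier. Protocol 8.1 states "The primary outcome is the elapsed time from random treatment assignment to the development of confirmed abnormal glucose tolerance or clinical diabetes", and Protocol 4.3 states that "study drug administration must occur within 4 weeks after randomization". Someone who is randomized, never starts drug and stays in follow-up can therefore have an endpoint that the intention-to-treat analysis counts and the FAS analysis drops.

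Three things are at stake:

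- The primary test is not tied to one set of people. If the two results differed, either could be reported with support from the SAP.
- Excluding randomized participants for post-randomization reasons is what the stated intention-to-treat rule is meant to prevent.
- If events are counted in everyone enrolled but analysed in the FAS, an analysis could contain fewer events than the number that triggered it.

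**Working it through.** **Which participants separate the two sets**

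| Participant | All randomized | FAS | Effect on the Cox comparison |
|---|---|---|---|
| Dosed and assessed | in | in | none |
| No follow-up after baseline, dosed or not | in, censored near time zero | out | essentially none |
| Never dosed, still followed | in, events count | out | can change the result |

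Only the last row matters.

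**The plan's own figure**

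Inputs from SAP section 5 and Protocol 8.4: 80 events, hazard ratio 0.50, two-sided 0.05, 201 randomized (135 and 66), stated power 83%. Schoenfeld's formula with critical value 1.96 gives

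power = Φ(√(d·p·(1−p))·ln 2 − 1.96).

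At d = 80 this is 0.832 with p = 2/3 and 0.829 with p = 135/201, so the stated 83% is reproduced for all randomized participants.

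**Power if some analysed events are lost**

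The documents give no FAS exclusion rate. I assume 1% to 5%, with a proportional share of events lost. The final boundary in SAP section 6 is 1.969, and p(1−p) = 2/9:

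power = Φ(√(d·2/9)·ln 2 − 1.969).

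| Share lost | Events analysed | Power |
|---|---|---|
| 0% | 80 | 0.830 |
| 1% | 79.2 | 0.826 |
| 2% | 78.4 | 0.822 |
| 5% | 76 | 0.810 |

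**Effect of one event near the boundary**

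With 80 events the log-rank variance is about 80 × 2/9 = 17.8, and its square root is 4.22.

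- Dropping one placebo event moves Z by (2/3)/4.22 = 0.158.
- Dropping one hydroxychloroquine event moves Z by (1/3)/4.22 = 0.079.

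A result close to 1.969 can therefore cross the boundary on one or two participants.

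**How often the two verdicts would differ**

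The simulation used 20,000 trials per case, with:

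- 135 against 66 participants and exponential event times;
- placebo event rate 40% at two years and 10% dropout at two years;
- uniform four-year accrual, stopping at the 80th event among all randomized;
- an unstratified score test, significant if |Z| > 1.969.

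An assumed 1%, 2% or 5% of participants were undosed but fully followed.

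| Case | 1% | 2% | 5% |
|---|---|---|---|
| HR 0.50, undosed keep their arm's hazard | 1.8% | 2.7% | 4.3% |
| HR 0.50, undosed in the active arm have the placebo hazard | 2.0% | 2.7% | 5.2% |
| HR 1.0 | 0.7% | 1.2% | 2.0% |

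Type I error was 4.8% to 5.0% for both sets. Exclusion was simulated as unrelated to prognosis, so these runs do not measure the bias that selective exclusion could cause.

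**The case against.** The best defence is that the two sets will almost coincide. Appendix 1 of the protocol puts randomization and first administration in one step, and Appendix 2, footnote 3, requires initial dosing at the baseline visit. The four-week allowance permits delay but does not show that anyone goes undosed. The passages on continued follow-up off drug (Protocol 4.5.1, 7.2.2 and 7.2.4.2) concern people who had started it. The post-baseline condition does little, because anyone with an OGTT-confirmed endpoint has been assessed. Masking and analysis as randomized also limit bias. All of this stands, and it is why the size is put as small.

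It can also be said that the protocol is softer than it looks. Section 8 qualifies its rule and defers to the SAP, and section 8.6 is about withdrawal. That is fair, but SAP section 2 has no such qualifier, so the conflict lies inside the document deferred to.

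Finally, section 7 is the only place that names a primary efficacy population, so a reader might let the specific statement override the general one. That is a possible reading, but no text gives it precedence, and it would contradict section 2 and the protocol's stated principle.

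The 1% to 5% share is an assumption. Disagreement between verdicts is not an error rate.

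**Conclusion.** The concern holds. The SAP is wrong as written: sections 2 and 7 give the primary analysis to two sets that the SAP itself treats as different, and nothing resolves it. It should be fixed, although the numerical effect is probably small. Under the assumed 1% to 5% shares, power falls by at most about 2 percentage points, and the verdicts differ in about 2% to 5% of trials at a hazard ratio of 0.50 and 0.7% to 2.0% under no effect. Those disagreement rates assume that every undosed participant is fully followed, which maximizes their influence for a given share; they are not a bound on the share. Any bias from exclusion related to prognosis is not quantified. The main cost is that the primary test lacks one fixed population.

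**What to change.** - In SAP section 7, item 1, name all randomized participants, analysed as randomized, as the single primary efficacy population, and repeat this in section 3.
- Keep the FAS as a sensitivity analysis.
- State that the 40 interim events and the 80 final events are counted in all randomized participants. SAP section 7, item 2, gives a different final trigger, 64 to 70 events in the placebo group. That is a separate conflict to reconcile, but the counting population should be stated whichever trigger is kept.
- In the same edit, correct the primary outcome sentence in SAP section 2, which describes the cohort by insulin autoimmunity where Protocol 8.1 refers to islet cell autoimmunity. It is probably a slip, but Protocol 3.5 admits some participants regardless of insulin autoantibody (mIAA) status.

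The cost is SAP wording only, with no change to data collection, sample size or boundaries. It should be done before unmasking so that results cannot influence the choice. If participants who were never dosed are not in fact followed, they are censored early and the change makes almost no numerical difference.
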